## Appendix 4. Sample SAS Code

### Sample SAS Code for Estimand 1 – Risk Difference using Chan and Zhang (1999)

```
PROC BINOMIAL DATA=<DATASET> GAMMA=0 ALPHA=<Value> OUT=<>;
  PD/EX ONE STD;
  PO <POPULATION VARIABLE>;
  OU <OUTCOME VARIABLE>;
RUN;
```

### Sample SAS Code for the Confidence Interval of a Binomial Proportion (Blyth-Still-Casella)

```
PROC BINOMIAL DATA=<DATASET> ALPHA=<value> OUT=<>;
  BI/BS;
  OU <RESPONSE VARIABLE>;
RUN;
```

### Sample SAS Code for the Confidence Interval of two Binomial Proportion (Minimum Risk)

```
PROC FREQ DATA= <DATASET>;
  TABLES <STRATA>*<TRT>*<EVENT> / COMMONRISKDIFF(CL=MR
  TEST=MR COLUMN=2 ) RELRISK ALPHA=<VALUE>;
  ods output CommonPdiff=<> CommonPdiffTests=<>
RUN;
```

### Sample SAS Code for Generalized Linear Mixed Model

```
PROC GLIMMIX DATA=<DATASET>;
  CLASS AVISIT <TRT> <STRATA> USUBJID;
  MODEL CRIT1FL(EVENT="Y")=<STRATA> <TRT>|AVISIT
  /ALPHA=0.05 DIST=BINARY DDFM = KR;
  RANDOM _RESIDUAL_ /SUBJECT = USUBJID TYPE=UN;
  LSMEANS <TRT>*AVISIT/ILINK COV DIFF CL ALPHA=<VALUE>;
RUN;
```

**Sample SAS Code for Estimand 2 ANCOVA**

```

libname c3941005 "/Volumes/app/..... /data_vai" ;
data ps;
  set c3941005.adps;
run;
data look;
  set ps;
  where param = "EASI02-Total Sum" and viswin ne .;
  keep subjid param paramn avisit age sex trta viswin visit xviswin aval base chg pchg
trtan;
run;
data ex1;
  set look;
  where upcase(avisit)='WEEK 12';
  regimen = "QD";
  if trtan = 1 then dose=0;
  if trtan = 2 then dose=0.01;
  if trtan = 3 then dose=0.03;
  if trtan = 4 then dose=0.06;
  keep subjid dose regimen chg aval base;
run;
proc means data=ex1;
  class regimen dose;
  var chg aval;
run;
proc sort data=ex1 out=ex2;
  *data must be sorted by regimen before use in proc mi;
  by regimen dose;
run;
*imputing aval=observed so range of endpoint 0-72 can be included in;
*mi procedure;
proc mi data=ex2 seed=1022 n impute=1000 out=outimp max=. 72 72 min=. 0 0;
  by regimen;

```

```
class dose;
monotone reg(aval= base/details);
mnar model( aval/modelobs = (dose="0"));
var base  aval;
run;
proc univariate data=outimp;
var aval;
histogram ;
run;
data outimp1;
  set outimp;
  chg = aval - base;**calculate chg from baseline
run;
proc sort data = outimp1 out = outimp2;
  by _imputation_ regimen dose subjid;
run;

proc mixed data=outimp2;
  by _imputation_;
  class dose regimen;
  model chg = base dose*regimen;
  lsmeans dose*regimen/ diff alpha=<Value>;
  ods output diffs=diffs lsmeans=lsmeans;
run;

data diffssout;
  set diffss;
  **only keep within regimen contrasts vs placebo;
  where regimen = _regimen and dose = 0;
run;
**now use mianalyze on lsmean differences;
**First sort by group, regimen and _dose (dose = 0 for all groups);
proc sort data=diffssout out=diffssout1;
```

```
by regimen _dose _imputation_;  
run;  
**now mianalyze by regimen and _dose;  
**NB mianalyze only uses estimates and standard errors not CI limits etc.;  
proc mianalyze data=diffsout1 alpha=<Value>;  
  by regimen _dose;  
  modeleffects estimate;  
  stderr stderr;  
  ods output parameterestimates=parameterestimates;  
run;
```

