## 4. ANALYSIS SETS (POPULATIONS FOR ANALYSIS)

Data for all participants will be assessed to determine if participants meet the criteria for inclusion in each analysis population prior to releasing the database and classifications will be documented per standard operating procedures. For participants with multiple enrollment, only the participant identifier and data under initial enrollment will be included and summarized. Data collected for other enrollments will be included only in listings and narratives. For IGA, PGA, EASI and PASI related endpoints that require qualified raters, evaluations at visits by non-qualified raters will be excluded.

Participant Analysis Set	Description
ITT Analysis Set	All participants randomly assigned to study intervention. Participants will be analyzed according to the randomized intervention.
Safety Analysis Set	All participants randomly assigned to study intervention who took at least 1 dose of study intervention. A randomized but not treated participant will be excluded from the safety analyses. Participants will be analyzed according to the intervention received.

Participant Analysis Set	Description
CCI	

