### **6.2.2. Continuous Secondary Endpoints**

Continuous secondary endpoints include percent CFB in EASI total score, CFB in PASI total score, and percent CFB in affected BSA.

- Estimand strategy: Secondary estimand ([Section 2.2.2](#)). This estimand is intended to provide an estimate of the treatment effect in the absence of prohibited medication use in a population that may or may not be fully compliant with the treatment.
- Analysis set: ITT Analysis Set ([Section 4](#)).
- Analysis methodology: A landmark analysis of these continuous endpoints at Week 12 will be performed by ANCOVA with baseline as a covariate. Missing data, except missing due to COVID-19 pandemic, will be imputed using a control-based imputation method. PROC MI will first be called to impute missing vehicle observations under the assumption data are missing at random (MAR) and impute

missing active treatment observations assuming they are similar to corresponding vehicle arm. The imputation will utilize ANCOVA model including baseline as a covariate fitted using only vehicle arm data. The analysis will combine the results from the multiple imputations using Rubin's rule's as implemented in SAS PROC MIANALYZE. MMRM models may also be used on observed data at all time points as sensitivity analyses. The fixed effects of treatment, visit, and treatment by visit interaction will be included. Baseline value will be included as a covariate. No adjustments for multiplicity will be made.

- Intercurrent events and missing data: A) Prohibited medication: all scores measured at time points after start date of the event for participants who receive prohibited medication post randomization will be excluded from the analysis and treated as missing scores. Missing scores will be imputed. B) Withdrawal and all other events leading to missing data, except COVID-19 pandemic: all missing scores will be imputed. C) COVID-19 pandemic: if a participant misses a visit due to COVID-19, he/she will be excluded from the analysis for that visit; If a participant discontinues treatment or withdraws from the study due to COVID-19, he/she will be excluded from the analyses after the treatment discontinuation visit or study withdrawal visit, respectively. D) Inadequate compliance – participants data will be used as recorded.

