### Sample SAS Code for Estimand 2 MMRM

```
proc mixed data=_dsnin order=internal alpha=<Value>;  
  by PARAMN;  
  class SUBJID AVISITN TRTPN;  
  model PCHG = BASE TRTPN AVISITN TRTPN*AVISITN /solution ddfm=kr;  
  repeated AVISITN/ participant =SUBJID type=un r rcorr;  
  /**try UN first, if not converged, will use CS***/  
  lsmeans TRTPN*AVISITN / diff cl alpha=<Value>;  
  ods output lsmeans=lsmeans diffs=diffs;  
run;  
/*For one-sided P-value calculation, the LOWER tail side should be used. */;
```

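### The sample E2 ANCOVA code does not match the specified ITT analysis: it takes the arm from `trtan`, and it imputes only participants who already have a Week 12 row

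*SAP*

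**What the plan says.** **Text.** SAP Section 6.2.2 covers percent change in EASI, change in PASI and percent change in affected BSA. It specifies "Analysis set: ITT Analysis Set". Section 4 defines that set: "All participants randomly assigned to study intervention. Participants will be analyzed according to the randomized intervention". Treatment received is used for the Safety set: "Participants will be analyzed according to the intervention received". Section 6.2.2 also gives three data rules:

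- missing Week 12 scores are multiply imputed, with active-arm values drawn from a model fitted to vehicle data;
- scores after prohibited medication become missing and are then imputed;
- visits missed because of COVID-19 are left out.

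Appendix 1 agrees (ITT, MI, ANCOVA).

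**ANCOVA code (SAP Appendix 4).** The only treatment variables kept are `trta` and `trtan`. Dose is built by "if trtan = 1 then dose=0" and three parallel lines. Rows must have a non-missing `viswin`, and are then cut by "where upcase(avisit)='WEEK 12". PROC MI follows, with an MNAR statement that models `aval` on vehicle observations.

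**MMRM code (SAP Appendix 4, same estimand).** The arm is TRTPN: "class SUBJID AVISITN TRTPN" and "model PCHG = BASE TRTPN AVISITN TRTPN*AVISITN /solution ddfm=kr".

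**The concern.** The main E2 analysis and its sensitivity analysis take the arm from different variables, and only the MMRM choice fits an ITT definition. If `trtan` is treatment received, a participant given the wrong product changes arm, and a randomised participant who was never dosed may have no arm at all. The second case can arise because the SAP's ITT set, unlike the Full Analysis Set in Protocol Section 9.2, does not require a dose.

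The row filter bears on missing data. E2 assumes that participants who leave end with vehicle-like scores. PROC MI fills blanks only in rows it is given. If a participant without a Week 12 assessment has no Week 12 row, nothing is imputed and that participant leaves the analysis. The estimate then describes participants with Week 12 data only, which is more favourable to active treatment than the question E2 asks.

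**Working it through.** The plan states no figure for this point, so there is none to reproduce. The check sets text against code and then sizes the consequence.

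**1. Arm variable.**

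| Source | Arm taken from |
|---|---|
| SAP Section 4, ITT set | randomised intervention |
| Appendix 4, E2 ANCOVA | `trtan` |
| Appendix 4, E2 MMRM | TRTPN |

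The documents do not define `trtan`; reading it as actual treatment rests on the usual naming convention. If nobody was mis-dispensed or left undosed, the two variables give the same result. If one of 40 AD participants randomised to active received vehicle and responded like vehicle, ITT keeps that participant in the active arm, and the active mean moves towards vehicle by 1/40 = 2.5% of the gap. The `trtan` version would not show this. With 30 per arm in PsO the figure is 1/30 = 3.3%.

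**2. Which rows reach PROC MI.** Appendix 3 assigns visits by study day, and Week 12 is days 79 to 99. An early-termination assessment before day 79 carries an earlier label. Such a participant has a Week 12 row only if a later visit, such as follow-up, falls in that window, or if the dataset was padded. The code has no padding step, and no document describes the structure of the input dataset.

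A related case is recorded in the SAP. Version 3 excludes PGA/PASI evaluations of 10 PsO participants at several visits because the rater was not qualified. Whether Week 12 is among those visits is not stated. If it is, deleting the row or blanking the score decides whether the value is imputed.

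**3. Size if the rows are absent.** Let D be the mean difference among participants with Week 12 data, and d the share of the active arm without it, with missingness unrelated to outcome.

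- Rows absent: nothing is imputed and the estimate is D.
- Rows present: imputing vehicle participants from vehicle leaves the vehicle mean unchanged on average. The active mean becomes (1 - d) × active + d × vehicle, so the estimate is (1 - d) × D.
- Ratio, absent to present: 1/(1 - d).

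A simulation of both cases used these inputs, none of them from the documents: 40 per arm; baseline mean 8 and SD 4; Week 12 mean 0.6 × baseline on vehicle and 0.3 × baseline on active; residual SD 3; values missing completely at random at the same rate in both arms; 300 replicates; 30 imputations. It analysed change from baseline, as the sample code does.

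| d | 1/(1 - d) | Rows absent | Rows present | Ratio | Mean values imputed, of 80 (rows present) |
|---|---|---|---|---|---|
| 0% | 1.00 | -2.448 | -2.448 | 1.00 | 0 |
| 5% | 1.05 | -2.392 | -2.274 | 1.05 | 3.9 |
| 10% | 1.11 | -2.392 | -2.152 | 1.11 | 8.0 |
| 20% | 1.25 | -2.359 | -1.892 | 1.25 | 15.9 |
| 30% | 1.43 | -2.334 | -1.634 | 1.43 | 23.9 |

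The absolute differences depend on the assumed inputs. The ratio follows the formula.

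The documents give no dropout rate, so d is shown as a range. Protocol Table 2 lists 40 and 30 per arm as completers, the same numbers the synopsis gives as randomised.

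**The case against.** The governing text is clear, and the code is labelled as a sample. It has unfilled value placeholders and a shortened path. It also maps a fourth treatment code to 0.06% while selecting EASI, although AD has no 0.06% arm. It must be adapted before it can run. The imputation block, with 1,000 imputations, bounds of 0 to 72 and a vehicle-based model, would have little purpose unless its author expected Week 12 rows with a missing score. The filters remove a placeholder row only if it lacks a window value or the Week 12 label.

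That stands against one inference a reader might draw, namely that E2 will in fact be run as-treated and close to complete-case. The documents do not show this: they report no mis-dispensed or undosed participant and say nothing of the dataset's structure.

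A reader might also infer from the missing prohibited-medication and COVID-19 steps that those rules will not be applied. This is weak evidence. The Appendix 4 samples are largely model calls on prepared data. The code for the primary endpoint has no non-responder step either, and nobody would conclude that the primary analysis ignores non-response.

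The objection does not remove the `trtan`/TRTPN conflict, which is visible on the page. Nor does it supply a statement, in text or code, that every ITT participant has a Week 12 row.

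**Conclusion.** The point holds as a mismatch between text and sample code in a secondary analysis. The arm variable is inconsistent with the ITT definition and with the MMRM code. Its numerical effect is zero unless a participant was mis-dispensed or not dosed, and is roughly 2.5% (AD) or 3.3% (PsO) of the treatment gap for one mis-dispensed participant whose response follows the product received.

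The loss of participants without a Week 12 record is a conditional risk. If placeholder rows are absent, the E2 difference is overstated by about 5%, 11% or 25% at 5%, 10% or 20% missing in the active arm. This assumes that missingness is unrelated to outcome and that d lies in that range. If the rows are present with blank scores, the code imputes them from vehicle as Section 6.2.2 intends and there is no overstatement.

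Only the continuous secondary endpoints are affected, and these carry no multiplicity adjustment. The primary IGA/PGA analysis does not use this code.

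**What to change.** In SAP Appendix 4, E2 ANCOVA code:

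1. Define dose from TRTPN, as the MMRM code already does.
2. Before PROC MI, build one Week 12 row for each ITT participant with a baseline, leaving `aval` missing where no score was observed.
3. Apply the Section 6.2.2 rules to that input: blank scores after prohibited medication and remove visits missed because of COVID-19.

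For items 2 and 3, a sentence stating that the input dataset is already built this way would serve equally well. That sentence should also say whether scores from non-qualified raters are kept as blank rows or deleted.

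The cost is about ten lines of sample code, or one changed variable plus a sentence. No protocol change is needed.

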### 9.3.5. Secondary Endpoint(s)/Estimand(s) Analysis

Binary secondary endpoints will be analyzed similarly to the primary endpoints.

A landmark analysis of continuous endpoints including percent change from baseline in EASI and change from baseline in PASI at Week 12, defined in [Section 9.1.1.2](#), will be performed by ANCOVA using the full analysis set with baseline as a covariate. Missing data, except missing due to COVID-19 pandemic, will be imputed using a control-based method, assuming participants have efficacy values similar to vehicle participants, and data are MAR. The imputation will utilize ANCOVA model including baseline as a covariate. The analysis will combine the results from the multiple imputations using Rubin's rule's as implemented in SAS PROC MIANALYZE. MMRM models may also be used on observed data at all time points as sensitivity analyses. The fixed effects of treatment, visit, and treatment by visit interaction will be included. Baseline value will be included as a covariate. No adjustments for multiplicity will be made.

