#### **Atopic Dermatitis:**

Treatment condition: received treatment: PF-07038124 ointment 0.01%, 0.03% or vehicle, without the benefit of additional prohibited medications and regardless of treatment compliance.

Population: Participants with mild or moderate AD as defined by inclusion and exclusion criteria.

Variables: Percent change from baseline in EASI total score and percent CFB in affected BSA at all study visit time points specified in SoA.

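### The SAP's sample ANCOVA code for Estimand 2 names EASI but models absolute change, whereas the atopic dermatitis endpoint is percent change

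*SAP*

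**What the plan says.** The text of both documents is consistent about the variable. SAP 6.2.2 states: "Continuous secondary endpoints include percent CFB in EASI total score, CFB in PASI total score, and percent CFB in affected BSA". The Estimand 2 definition for AD in SAP 2.2.2 gives the variables as "Percent change from baseline in EASI total score and percent CFB in affected BSA at all study visit time points". Protocol 9.3.5 plans "A landmark analysis of continuous endpoints including percent change from baseline in EASI and change from baseline in PASI at Week 12", analysed by ANCOVA with baseline as covariate. SAP Appendix 1 lists percent change in EASI and change in PASI for both the multiple-imputation ANCOVA and the observed-case MMRM. SAP 2.1 declares no modification to the protocol's analysis.

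The sample code for the Estimand 2 ANCOVA in Appendix 4 differs. It selects the EASI total and no other parameter. Before imputation it reduces the data with "keep subjid dose regimen chg aval base", so `pchg` is lost. After PROC MI it recomputes only absolute change and fits "model chg = base dose*regimen". It then retains the differences satisfying "where regimen = _regimen and dose = 0".

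The MMRM sample code that follows uses percent change (`PCHG`) as the response. The appendix closes, after the MMRM block, with the comment "For one-sided P-value calculation, the LOWER tail side should be used".

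**The concern.** A programmer who follows the ANCOVA block for EASI will produce a treatment difference in EASI points, while the endpoint, the estimand and the results tables call for percentage points. In an average of absolute changes, each participant's percent change is weighted by his or her baseline score, so participants with high baselines dominate. The entry criteria (IGA 2 or 3, affected BSA 5% to 40%) allow baselines to differ considerably.

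The two blocks also disagree with each other. If each were used as printed for EASI, the main analysis and its MMRM sensitivity analysis would be on different scales, and the second could not show whether the first is robust. The MMRM block has the reverse fault for PASI, where absolute change is the endpoint.

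The direction of the retained contrasts is a smaller matter. They are vehicle minus active and the code does not label them. A reader expecting dose minus vehicle would see the sign reversed.

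**Working it through.** No sample size, power or alpha in the documents depends on this point, so there is no stated figure to reproduce. The check is a trace of the code, followed by illustrations whose inputs are assumed because the documents give no baseline EASI distribution.

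**1. Response variable**

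| Place | EASI | PASI |
|---|---|---|
| Protocol 9.3.5 | percent change | absolute change |
| SAP 2.2.2 (Estimand 2) and 6.2.2 | percent change | absolute change |
| SAP Appendix 1, ANCOVA and MMRM rows | percent change | absolute change |
| SAP Appendix 4, ANCOVA code | absolute change | not named |
| SAP Appendix 4, MMRM code | percent change for every parameter | percent change for every parameter |

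Imputing the raw score is deliberate, since a code comment cites the 0 to 72 range, and it is sound. The fault is that the derivation after imputation stops at `aval` minus `base`.

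**2. Why one scale cannot be read off the other** (assumed baselines)

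Absolute change = baseline × percent change / 100.

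- A 75% fall: 4 × (−0.75) = −3; 8 × (−0.75) = −6; 16 × (−0.75) = −12 points.
- Two participants with baselines 4 and 16 who change by −70% and −30%: mean percent change −50%; mean absolute change (−2.8 − 4.8)/2 = −3.8 points.
- The same two with the responses exchanged: mean percent change still −50%; mean absolute change (−1.2 − 11.2)/2 = −6.2 points.

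The same mean percent change thus corresponds to different mean absolute changes.

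**3. Simulated two-arm ANCOVA** (300 runs per row, medians)

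Assumed: 40 per arm; log-normal baseline EASI with median 7 and log-scale SD 0.5; SD of percent change 35 points; vehicle mean −30%; values truncated at −100%.

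| Active mean | Active minus vehicle, EASI points | Active minus vehicle, percentage points | One-sided p, absolute | One-sided p, percent |
|---|---|---|---|---|
| −50% | −1.48 | −19.0 | 0.0133 | 0.0069 |
| −60% | −2.22 | −28.3 | 0.0005 | 0.0001 |
| −70% | −2.94 | −36.9 | <0.0001 | <0.0001 |

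The data were generated with a constant percent effect, which favours the percent scale. The table shows that estimates and p-values differ; it does not show that one scale is always the more powerful.

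**4. Contrast direction**

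Vehicle is coded dose 0, the lowest class level. LSMEANS with DIFF forms the earlier level minus the later one. The retained rows have dose 0 as first member, and a code comment confirms that this holds for all groups. The output is therefore vehicle minus active. Improvement is a negative change, so a benefit appears as a positive number.

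For a benefit of 1.960 standard errors:

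- active minus vehicle, z = −1.960, lower tail 0.025;
- vehicle minus active, z = +1.960, lower tail 0.975;
- two-sided p-value 0.05 in both cases, with the same interval width.

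The MMRM code does not fix the order either. If its treatment variable is numbered as in the ANCOVA block, with vehicle first (an assumption), its differences are also vehicle minus active.

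**The case against.** The best defence is that this is sample code and the governing text is clear. The endpoint is stated correctly in several places and nowhere does the text call for absolute change in EASI. The block looks like a template shared between indications: it maps a 0.06% arm that exists only in psoriasis, its 0 to 72 limits suit PASI as well as EASI, absolute change is right for PASI, and it contains placeholders. Dataset names also fail to match between steps, although that may come from the PDF reading. On this view each block shows one response as an example, and Appendix 1 gives the same endpoint for both models.

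Much of this stands. It means the intended endpoint is not in doubt, and it would be wrong to infer that the AD analysis is planned, or will be reported, on absolute change. It does not clear the code. EASI is the only parameter the ANCOVA block names, absolute change is wrong for it, and nothing in the appendix tells the programmer which variable belongs to which endpoint.

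A reader might also infer that the one-sided p-values for these endpoints will be reversed. The documents do not support that. The lower-tail comment follows the MMRM block and the ANCOVA block names no tail. SAP 5.2.2 asks for p-values without giving a side, and 6.2.2 lists LS means, differences and 95% confidence intervals. The one-sided 0.025 level in SAP 5.1 belongs to the primary hypotheses. Nor does SAP 5.2.2 require dose minus vehicle: it refers to differences between each dose and vehicle, and 6.2.2 to each pair of groups, with no direction fixed. The reversal would arise only if a one-sided p-value were reported and the MMRM comment were carried over to the ANCOVA contrasts.

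**Conclusion.** The variable error holds: as printed, the Estimand 2 ANCOVA code analyses absolute change in EASI, while the protocol and the SAP text define the AD endpoint as percent change. The MMRM sample code is inconsistent with it and would be wrong for PASI. This follows from reading the code and needs no assumption. The size of the effect on a result cannot be given, because no baseline EASI distribution is stated; the figures above are illustrations on assumed values.

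The contrast direction is a matter of labelling. It rests on the standard LSMEANS ordering and the code's own comment.

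The scope is narrow: sample code for a secondary endpoint without multiplicity adjustment. The primary IGA and PGA analyses, their Type I error control and the sample size do not use this code. It should be corrected because it is the only worked specification of the imputation and ANCOVA steps.

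**What to change.** In SAP Appendix 4:

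- After PROC MI, derive `pchg = 100*(aval - base)/base`. Model `pchg` for EASI and affected BSA, and keep `chg` for PASI. Continue to impute the raw score.
- Use the same endpoint-specific response in the MMRM code: percent change for EASI and BSA, absolute change for PASI.
- Output dose minus vehicle, by reversing the sign or setting the reference level, or else label the contrasts as vehicle minus active. Do this for both models.
- If any one-sided p-value is to be reported, state the tail next to the contrast it applies to. The lower tail suits dose minus vehicle.

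The cost is a few lines of sample code. No endpoint, estimand, data collection or sample size changes, and the protocol needs no amendment because its text is already right.
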